### 4.8.2. Adverse Events

Adverse events will be coded using the Medical Dictionary for Regulatory Activities (MedDRA) and displayed in tables and listings using System/Organ/Class (SOC) and Preferred Term.

Analyses of adverse events will be performed for those events that are considered treatment emergent (TEAEs), where treatment emergent is defined as AEs with a start date on or after the first dose of extension study drug through 30 days after discontinuation of study drug or Month 12 visit date, or any event that was present at Month 6 but worsened in intensity or was subsequently considered drug-related by the investigator through the end of the extension study.

Adverse Event tables will be presented for the following periods: Month 6 to Month 12 (Extension treatment period) and Month 12 to Month 6 ExFU (Extension follow-up period) as defined in section 4.2.12.

Adverse events starting more than 30 days after end of treatment will be considered as post-treatment AE.

For each of these 2 study periods, an overall summary table will be prepared presenting, by treatment group, the number and percentage of subjects with

- any AE,
- any TEAE,
- any post-treatment AE (displayed only for the Extension follow-up period),
- Severe TEAE,
- any TEAE assessed by the Investigator as related to Linzagolix ((definite, probable, or possible relationship),
- any TEAE assessed by the Investigator as related to add-back therapy ((definite, probable, or possible relationship),
- any TEAE leading to permanent discontinuation of IMP,
- any serious adverse event (SAE),
- any serious treatment emergent adverse event (Serious TEAE),
- any serious treatment emergent adverse event (SAE) related to Linzagolix,
- any serious treatment emergent adverse event (SAE) related to add-back therapy,
- any fatal TEAE (where outcome is "Fatal")

CRS-BS-TP-000005 V 1.0

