13.5.3 Safety Analysis

Summaries will be performed using the Extension Safety Analysis Set and the Follow-up Extension Analysis Set.

Data from both the main study and the extension study will be summarized.

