## 1.2. **Objectives of Statistical Analysis**

Following the early termination of the main study (18-OBE2109-002), this extension study was early terminated as well and due to the number of subjects randomized being substantially lower than the target number if the study had been fully enrolled, this statistical analysis plan (SAP) is focused on the safety analysis and all safety and efficacy data will be presented in listings. Consequently, this SAP is designed to outline the methods to be used in the analysis of study data to answer the safety and tolerability objectives.

The primary objective of this extension study was to assess the maintenance of efficacy of linzagolix administered orally once daily for up to an additional 6 months (for up to 12 months of treatment in total) in women who had already completed 6 months of linzagolix treatment at a dose of 75 mg alone or of 200 mg in combination with add-back therapy (estradiol (E2) 1 mg / norethisterone acetate (NETA) 0.5 mg) in the management of moderate to severe endometriosis-associated pain (EAP) in women with surgically confirmed endometriosis. The two co-primary efficacy endpoints were clinically meaningful reduction over the last 28 days of randomized treatment up to the Month 12 visit, along with a stable or decreased use of analgesics for EAP, for 1) dysmenorrhea (DYS) and for 2) non menstrual pelvic pain (NMPP).

Sponsor:	ObsEva		
Protocol:	19-OBE2109-00	5	
Document Version No.:	1.0	Document Date:	18-MAY-2021

Secondary objectives included evaluation of efficacy over the last 28 days of randomized treatment up to the Month 12 visit based on the following parameters: evaluation of pain associated with sexual intercourse (dyspareunia) and defecation (dyschezia), difficulty of doing daily activities, analgesic use, assessment of subject perception of severity, change in uterine bleeding, Quality of Life (QoL) questionnaires, pharmacoeconomic burden of endometriosis by assessing changes in patient productivity, assessment of endometriosis-related number of non-study health visits, number of days in hospital and type of medical procedures performed during the Treatment Period.

Safety and tolerability objectives included assessment of bone mineral density (BMD), endometrial health, cardiac safety including QT interval prolongation, standard laboratory safety parameters, gynecological assessments and adverse event (AE) frequency including specific hypoestrogenic AEs.

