### 4.8.1. Extent of treatment exposure and compliance on the extension study

### 4.8.1.1. Extent of treatment exposure in the extension study

Duration of treatment (weeks) will be summarized for each treatment group. Duration is defined as: [(date of last extension treatment administration as described in section 4.2.12) - (date of first administration in extension as collected in eCRF) +1] / 7.

Time on extension study (weeks) will be summarized for each treatment group, defined as: [(end of extension study date as described in section 4.2.12) – (date of first administration in extension as collected in eCRF) +1.]/7

Exposure data will be reported in listings.

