#### Page **39** of **66**

Sponsor:	ObsEva		
Protocol:	19-OBE2109-00	5	
Document Version No.:	1.0	Document Date:	18-MAY-2021

In these tabulations, each subject will contribute only once (i.e., via the most related occurrence or the most intense occurrence) to each of the incidence rates in the descriptive analysis, regardless of the number of episodes experienced.

Adverse events are summarized by subject incidence rates, therefore, in any tabulation, a subject contributes only once to the count for a given adverse event (SOC or preferred term).

The number and percentage of subjects with any treatment-emergent adverse event will be summarized by treatment group and by SOC and PT.

If serious TEAEs are observed in the study, the number and percentage of subjects with any non-serious treatment-emergent adverse event will be summarized by treatment group.

Serious TEAE, TEAE assessed by the Investigator as related to treatment (definite, probable, or possible relationship), TEAE leading to permanent discontinuation of IMP, TEAE leading to permanent discontinuation of IMP leading to death and post-treatment AE will be only listed due to the low number of subjects included in the extension study.

The number of events will be also displayed for summaries on TEAE and for analysis of TEAE and nonserious TEAE by SOC and PT.

The ongoing status of each Adverse Event will be derived based on Adverse Event Outcome as the following:

AE Outcome	AE Ongoing Status
Fatal	Νο
Not recovered/not resolved	Yes
Recovering/resolving	Yes
Recovered/resolved	Νο
Recovered/resolved with sequelae	Νο
Unknown	Unknown
Missing	Missing

The ongoing status collected in eCRF will be ignored.

No formal hypothesis-testing analysis of adverse events incidence rates will be performed.

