## 5. CHANGES TO PLANNED ANALYSES

Following the early termination of the study and due to the number of subjects randomized being really less than the target number if the study had been fully enrolled, the analyses planned in the protocol on efficacy and pharmacokinetic assessments have been removed and only listings (if data available) for these assessments will be displayed. The statistical analysis plan (SAP) will be focused on the safety analysis.

For safety endpoints, the endpoint "Time to the first post-treatment menses" was initially planned in the protocol, but will not be described in this SAP, because the study was stopped prematurely and all subjects couldn't be followed to evaluate this endpoint.

Sponsor:	ObsEva				
Protocol:	19-OBE2109-005				
Document Version No.:	1.0 Document Date: 18-MAY-2021				

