### Section 14.3.1 Adverse Events

- Table 14.3.1.1.1 Summary of Treatment-Emergent Adverse Events from Month 6 to Month 12 Extension Safety Analysis Set
- Table 14.3.1.1.2 Summary of Treatment-Emergent Adverse Events from Month 12 to Month 6 ExFU - Follow-up Extension Safety Analysis Set
- Table 14.3.1.2.1 Treatment-Emergent Adverse Events by MedDRA SOC and Preferred Term from Month 6 to Month 12 Extension Safety Analysis Set
- Table 14.3.1.2.2 Treatment-Emergent Adverse Events by MedDRA SOC and Preferred Term from Month 12 to Month 6 ExFU Follow-up Extension Safety Analysis Set
- Table 14.3.1.3.1 Non-Serious Treatment-Emergent Adverse Events by MedDRA SOC and Preferred Term from Month 6 to Month 12 Extension Safety Analysis Set (if applicable)
- Table 14.3.1.3.2 Non-Serious Treatment-Emergent Adverse Events by MedDRA SOC and Preferred Term from Month 12 to Month 6 ExFU Follow-up Extension Safety Analysis Set (if applicable)

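### No adverse-event or exposure summary in this SAP covers the continuing groups' whole time on drug, and Section 5 does not declare the narrower scope

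*SAP*

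**What the plan says.** SAP 4.8.2 uses one definition for all four combined treatment groups: "treatment emergent is defined as AEs with a start date on or after the first dose of extension study drug through 30 days" after the end of treatment. Events already ongoing at extension entry are added only through a carry-over clause, "any event that was present at Month 6 but worsened in intensity or was subsequently considered drug-related by the investigator". SAP 4.8.1.1 computes treatment duration from the "date of first administration in extension as collected in eCRF".

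Appendix B (Section 14.3.1) lists six adverse-event tables. Three are of the type "Summary of Treatment-Emergent Adverse Events from Month 6 to Month 12"; the other three cover Month 12 to Month 6 ExFU. SAP 4.8.2 also says that in any tabulation "a subject contributes only once to the count for a given adverse event (SOC or preferred term").

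Protocol 13.5.3 states for safety: "Data from both the main study and the extension study will be summarized". SAP 1.2 undertakes to set out differences from the protocol. SAP Section 5 then records that "the analyses planned in the protocol on efficacy and pharmacokinetic assessments have been removed", together with the loss of the time-to-first-menses endpoint, and nothing else.

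**The concern.** The four groups stand side by side in the same tables, but the same calendar window is a different stage of treatment in each. Continuing subjects were already on the same active drug in the main study; switch subjects took placebo there and start active drug at Month 6. So the Month 6 to 12 columns show early treatment for one pair of groups and late treatment for the other.

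After early termination, "this statistical analysis plan (SAP) is focused on the safety analysis" (SAP 1.2), and protocol 5.6 gives data for up to 12 months as the reason for the study. A reader would want one figure: what share of subjects treated for that long had a given event, and over how much drug exposure. This SAP does not produce it. The protocol's own account of the Phase 2b extension (5.5.3) does give such a figure, for 52 weeks.

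**Working it through.** **Inputs.** A month is 28 days, Month 6 is Day 169 and Month 12 is Day 337, counted from main-study Day 1 (protocol 10.2 and 10.2.1.1; SAP Table 3). The last dose is taken the day before the Month 12 visit, so Day 336 (protocol 10.2.1). Group definitions are in SAP 3.1 and 4.2.1.

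**Figures in the documents, reproduced.** Planned entry: 450 × 0.80 = 360 and 360 × 0.80 = 288, as stated. Phase 2b: 616/846 = 72.8% and 154/176 = 87.5%, as stated. The extension plans no hypothesis test, so no power figure bears on this point.

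**Treatment duration by the SAP formula.** (336 − 169 + 1)/7 = 168/7 = 24.0 weeks in every group.

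**Treatment duration from first active dose.**
- Switch groups: 168/7 = 24.0 weeks, unchanged.
- Continuing groups: (336 − 1 + 1)/7 = 336/7 = 48.0 weeks.

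**Share of active days inside the Month 6 to 12 window, full course.**
- Switch: 168/168 = 100%, for subjects who took active drug throughout.
- Continuing: 168/336 = 50%.

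**After early stopping.** A continuing subject with *d* extension days has *d*/(168 + *d*) of her active days covered:
- *d* = 28: 28/196 = 14.3%
- *d* = 84: 84/252 = 33.3%
- *d* = 168: 168/336 = 50.0%

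So 50% is the ceiling on the planned schedule. The treatment-emergent definition runs 30 days past the last dose (336 + 30 = Day 366), and that tail falls in the follow-up tables. The carry-over clause lets some earlier-onset events in. Neither restores the first 24 weeks.

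**Why period tables cannot be added.** Each subject counts once per table. If 20% of the same subjects had an event in each of two periods (an assumed value), the share with at least one event lies anywhere from 20% (the same subjects) to 40% (different subjects). The tables do not show the overlap.

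**Illustration of timing, not an estimate.** In Phase 2b, 846 − 616 = 230 TEAEs (27.2%) came after week 24. Per week that is 616/24 = 25.7 against 230/28 = 8.2, a ratio of 3.1. Of 61 hot flush events, 2 were in the extension, leaving 59 (96.7%) outside it. Those data pool all groups, including a placebo/100 mg group and a 200 mg group reduced to 100 mg.

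**The opposite bias.** Crude percentages over unequal follow-up also mislead. At a constant event rate, a 24-week incidence *p* becomes 1 − (1 − *p*)² over 48 weeks: 10% becomes 19%, 20% becomes 36% and 40% becomes 64%, with no difference in rate.

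**The case against.** The strongest reply has four parts.

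- **The window is disclosed.** The table titles name the period, the groups are labelled by treatment in both studies, and the exposure section is headed as extension-only. This stands. A reader might infer that the tables hide the missing weeks; the documents do not support that.
- **The main study has its own SAP.** SAP 4.2.12 assigns data to one study or the other at Month 6, so main-study events may well be summarized in the main-study report. That plan was not available. One cannot infer that main-study events go unreported. What remains is the lack of a combined subject incidence, which separate period tables cannot supply.
- **Protocol 13.5.3 promises no cumulative table.** True, and this SAP does use main-study data: baseline characteristics, and changes from main-study baseline for BMD, laboratory values, vital signs, ECG and TVUS. C-SSRS can also reach back, because answers covering the time since study start count (SAP 4.8.10). It would be wrong to call the whole safety analysis extension-only. The gap concerns adverse events and exposure, where early termination explains the dropped efficacy and PK analyses but no reason is given for this narrowing.
- **Numbers are small and the tables descriptive.** This stands against requiring exposure-adjusted rates for every SOC and preferred term. It does not stand against one cumulative table, since the SAP already produces SOC/PT tables for each period.

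All on-study events are also listed. A listing is not an incidence, and the text does not say whether it includes main-study events.

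**Conclusion.** The point holds as a gap in reporting, worth closing because closing it is cheap. This SAP gives neither subject incidence of adverse events nor total active exposure for the groups treated for up to 48 weeks. It summarizes at most 168 of their 336 active days, falls short of protocol 13.5.3 and does not say so in Section 5.

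The 50% rests on the planned visit days and on doses taken as assigned. The 100% for switch subjects does not apply to a subject who actually took placebo in both studies; SAP 3.1 places her in the Placebo / LGX 75 mg group although she has no active days.

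A reader might go further and conclude that continuing columns will look safer by some known amount, or that about 73% of events will be missing. The documents do not support a size: the Phase 2b timing comes from other regimens, and no between-group comparison is planned here.

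**What to change.** - Add one TEAE overview table and one SOC/PT table by combined actual treatment group, running from first active dose to 30 days after last dose. First active dose means the main-study first dose for continuing groups and the first extension dose for switch groups. Re-anchor the carry-over clause at the same dose.
- Add total active exposure to the exposure table (14.1.11.1).
- Show total person-time beside the crude percentages, with an exposure-adjusted rate at least for any TEAE and for hot flush, because follow-up is up to 48 against 24 weeks.
- Footnote that continuing subjects are those who completed 6 months on drug, so earlier discontinuations are not in these columns.
- Leave actual Placebo/Placebo subjects out of the new tables, since they have no first active dose, and footnote them.
- Keep the Month 6 to 12 tables.
- In Section 5, declare that the period adverse-event and exposure summaries are extension-only, and cross-refer to the main-study report.

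Cost: two descriptive tables and one exposure line. Main-study events must be coded in MedDRA 23.0, the version set in SAP 4.2.2. The two databases lock together (SAP 2.3.2), and the onset-date imputation rules (4.2.8.1) already use both first-dose dates. With few subjects, the cumulative percentages will be imprecise.

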#### Page **39** of **66**

Sponsor:	ObsEva		
Protocol:	19-OBE2109-00	5	
Document Version No.:	1.0	Document Date:	18-MAY-2021

In these tabulations, each subject will contribute only once (i.e., via the most related occurrence or the most intense occurrence) to each of the incidence rates in the descriptive analysis, regardless of the number of episodes experienced.

Adverse events are summarized by subject incidence rates, therefore, in any tabulation, a subject contributes only once to the count for a given adverse event (SOC or preferred term).

The number and percentage of subjects with any treatment-emergent adverse event will be summarized by treatment group and by SOC and PT.

If serious TEAEs are observed in the study, the number and percentage of subjects with any non-serious treatment-emergent adverse event will be summarized by treatment group.

Serious TEAE, TEAE assessed by the Investigator as related to treatment (definite, probable, or possible relationship), TEAE leading to permanent discontinuation of IMP, TEAE leading to permanent discontinuation of IMP leading to death and post-treatment AE will be only listed due to the low number of subjects included in the extension study.

The number of events will be also displayed for summaries on TEAE and for analysis of TEAE and nonserious TEAE by SOC and PT.

The ongoing status of each Adverse Event will be derived based on Adverse Event Outcome as the following:

AE Outcome	AE Ongoing Status
Fatal	Νο
Not recovered/not resolved	Yes
Recovering/resolving	Yes
Recovered/resolved	Νο
Recovered/resolved with sequelae	Νο
Unknown	Unknown
Missing	Missing

The ongoing status collected in eCRF will be ignored.

No formal hypothesis-testing analysis of adverse events incidence rates will be performed.

# Cytel

## Statistical Analysis Plan

Sponsor:	ObsEva		
Protocol:	19-OBE2109-005		
Document Version No.:	1.0	Document Date:	18-MAY-2021

All adverse events occurring on study will be listed in subject data listings.

By-subject listings also will be provided for the following: Treatment Emergent Adverse event, serious Treatment Emergent adverse events; Treatment Emergent adverse events leading to permanent discontinuation of IMP and leading to permanent discontinuation of IMP leading to death.

## 4.8.3. Bone Mineral Density (BMD) by DXA

BMD of femoral neck, total hip and lumbar spine will be assessed by DXA at Baseline, Month 9 (if required) Month 12 and Month 6 of the extension follow-up (if required). Unacceptable DXA assessments (accepted="No") will not be summarized (hip, spine and femur considered separately).

In case of repeated values due to BMD loss ≥5%, the initial scan will be used in summaries. Initial and repeated scan values will be reported in the listings.

Calibrated values will be used if available, otherwise initial values will be considered.

BMD, expressed as both absolute values and Z-scores will be summarized at each visit in terms of actual values, changes from baseline, changes from baseline 2 (only for the subjects who are in the placebo arm in the main study) for each anatomic location. For absolute values only, percent change from baseline, percent changes from baseline 2 (only for the subjects who are in the placebo arm in the main study) and 95% confidence interval for the mean percent change from baseline and for the mean percent change from baseline 2 within each group will be produced at each time point.

The definition of both baselines are described in section 4.2.11.

Percent change from baseline and percent change from baseline 2 to Month 9, Month 12 and Month 6 extension follow-up will be described and will also be summarized in categories of percentage with the following classes:

- No change or increase,
- Decrease ≤ 3%,
- Decrease > 3% and  $\leq 5\%$ ,
- Decrease > 5% and  $\leq$  7%,
- Decrease > 7% and  $\leq$  8%,
- Decrease > 8%.

All data will be listed.

CRS-BS-TP-000005 V 1.0

Sponsor:	ObsEva		
Protocol:	19-OBE2109-00	5	
Document Version No.:	1.0	Document Date:	18-MAY-2021

#### 4.8.4. Laboratory Data

Clinical laboratory values will be expressed using conventional SI units.

Hematology, coagulation parameters, chemistry and lipids were assessed at screening and at each visit during the extension treatment period (from M7 to M12), as well as at the M1 ExtFU and M3 ExtFU visits.

E2, progesterone (P4) and LH were assessed at each visit during the extension treatment period (from M6 to M12), as well as at M1 ExtFU and M3 ExtFU visits.

Serum levels of sex hormone-binding globulin (SHBG) were assessed on Month 6, Month 9 and Month 12 visits.

Blood samples were to be analyzed by the central laboratory. Due to the covid-19 situation, some samples may be collected by local laboratories.

For Hematology, coagulation parameters, chemistry and lipids, the actual value, change from baseline and change from baseline 2 (only for the subjects who are in the placebo arm in the main study) will be summarized for each visit for each treatment group. In the event of repeated values, the last non-missing value per study day/time will be used.

Evaluation of shifts for changes from baseline and for changes from baseline 2 (only for the subjects who are in the placebo arm in the main study) to all visits according to the normal ranges with categories "Low", "Normal", "High" and according to normal/abnormal/abnormal clinically significant information collected otherwise, will be provided.

For Liver Function Test (LFT) parameters (ALT, AST, ALP, total bilirubin, direct bilirubin, indirect bilirubin, GGT, LDH, albumin and Creatine Kinase), evaluation of shifts for changes from baseline will be extended by the worst (highest) on-treatment value (including unscheduled assessments) according to the normal ranges with categories "Low", "Normal", "High" will be provided.

For the lipid panel (Triglycerides, HDL, LDL, Total Cholesterol, LDL/HDL ratio), the percent change from baseline and the percent change from baseline 2 (only for the subjects who are in the placebo arm in the main study) to each on-study visit will also be summarized.

For serum levels of P4, SHBG and LH, only the actual values at each time point will be summarized. Note: in the event of repeated values, the last non-missing value per study day/time will be used.

Note that no serum levels of E2 is measured for subjects in extension study due to the early termination study.

For P4, since P4 above 10 nMol/L may suggest luteal activity and hence ovulation, the proportion of subjects with P4 >10.0 nMol/L at least once from Month 6 to Month 12 will also be provided in tables.

The number and percentage of subjects with cholesterol values in the following categories

• LDL ≥ 160 mg/dL

